#### 1.2 Study Rationale

Approximately 40% to 60% of patients with T1DM use continuous subcutaneous insulin infusion (CSII) devices, commonly referred to as insulin pumps (Umpierrez et al. 2018, Miller et al. 2015). CSII devices are computerized devices programmed to deliver an RAA under the skin continuously throughout the day via a catheter attached to a person's abdomen. When used in tandem with continuous glucose monitoring (CGM) this is a closed-loop system. Hybrid closed-loop systems are characterized by the coexistence of algorithm-driven automated insulin delivery (AID) for basal insulin coverage combined with manual mealtime bolus insulin doses.

The current study aims to evaluate mealtime use of Afrezza in adults ≥18 years of age with T1DM who currently use AID. In this study, Afrezza-treated subjects will use two different methods for basal insulin delivery (subcutaneous [SC] injection of long-acting insulin or an AID system with RAA) compared to a control group (without Afrezza) of patients on an AID system with RAA.

Subjects will administer their initial Afrezza dose based on the subject's current insulin-to-carbohydrate (I:CHO) ratio multiplied by 2 and rounded down to the nearest Afrezza dose size, subject to Investigator discretion, but not exceeding 24 units of Afrezza. Pooled Afrezza trial data suggests that subjects achieve similar glycemic control with a dose ratio of 1.5- to 2-fold the equivalent unit value of a subcutaneous insulin analog in head-to-head comparisons (Kendall et al. 2020, Grant et al. 2019), which is significantly higher than the dose conversion in the label. Additionally, a proof-of-concept study was done with 20 patients demonstrating improved postprandial glucose excursions (PPGE) with the higher dose of Afrezza compared to the current label (Afrezza 2020). This higher initial conversion dose of Afrezza will be used for the first dose under medical supervision in the clinic.

#### 1.3 Risks and Benefits

#### 1.3.1 Afrezza

Clear benefits of Afrezza include faster onset of insulin response, ability to administer insulin at mealtimes, lower risk of hypoglycemia and fewer injections compared to subjects using RAAs injected subcutaneously for post-prandial control.

The following safety risks have been identified through evaluation of all currently available data with Afrezza:

#### Important identified risks

- Bronchospasm in subjects with underlying chronic obstructive lung disease
- Severe hypoglycemia

Confidential Page 18 of 70

Hyperglycemia during initiation of treatment due to inadequate conversion of RAA dose

### Important potential risks

- Diabetic ketoacidosis
- Hyperglycemia during acute illness or change of treatment
- Lung cancer: Data are insufficient to determine whether Afrezza has an effect on lung or respiratory tract tumors. In subjects with active lung cancer, a prior history of lung cancer, or in subjects at risk for lung cancer, the Investigator considers whether the benefits of Afrezza use outweigh this potential risk.

Further information on the benefits and risks of Afrezza are provided in the Investigator's Brochure (IB) and the Afrezza prescribing information (Afrezza 2020).

#### 1.3.2 Insulin Degludec

Subjects who are randomized to treatment with Afrezza in combination with a basal insulin will discontinue using their insulin pump and inject insulin degludec for basal insulin coverage. During the transition period, there is a risk of increased hyperglycemia and/or hypoglycemia while the basal insulin dose is optimized. To mitigate the risk to subjects in this study, subjects will be provided training in the clinic and frequent telephone visits will occur in the first 21 days after randomization.

See the prescribing information for Tresiba for a complete list of risks (Tresiba 2019).

# 1.3.3 Continuous Glucose Monitoring

CGM will be used in this study to enable real-time display of glucose values. Subjects will wear a blinded Dexcom G6 Professional (Dexcom G6 Pro) between screening and randomization and during the last 10 days of the study, in addition to their own personal CGM. Subjects will be provided training in the clinic for how to operate the Dexcom G6 Pro. Additionally, subjects will measure their glucose throughout the study using an unblinded CGM system (sensors, transmitter) and glucose meters, if required.

Subjects will also be instructed to measure glucose values using a blood glucose meter (self-monitored blood glucose [SMBG] value), as required by their personal CGM system, and to confirm glucose levels when their CGM is <70mg/dL and anytime their CGM reading does not match their symptoms or expectations.

Use of CGM is associated with a low risk for developing a local skin infection at the site of the CGM sensor placement. Itchiness, redness, bleeding, and bruising at the insertion site may occur as well as local tape allergies. CGM sensors may fracture in situ on rare occasions. In the rare instances when this has occurred in the past, consulting physicians and surgeons have recommended not to remove the wire fragment from beneath the skin as long as there are no symptoms of infection or inflammation. In the event that signs and/or symptoms of infection or inflammation arise such as redness, swelling, and pain subjects should consult with the Investigator or prescribing physician for the best course of action. If there is no portion of the

Confidential Page 19 of 70

broken sensor wire fragment visible above the skin, attempts to remove it without medical guidance are not advised.

For a complete list of risks for Dexcom G6, refer to the Dexcom G6 Pro User Guide (Dexcom 2020). For a complete list of risks for the subject's personal CGM that they will continue to use during the study, refer to the corresponding user guide.

Confidential Page 20 of 70

#### 2 STUDY OBJECTIVES

#### 2.1 Primary Objective

The primary objective of this study is:

- To evaluate the change in HbA1c from baseline to end of study in adults ≥18 years of age with T1DM for each of the three following groups:
  - Afrezza + AID: Afrezza for bolus (mealtime) in combination with use of a CSII pump with an AID algorithm using a RAA for basal and correction insulin coverage
  - Afrezza + Insulin Degludec: Afrezza for bolus (mealtime and correction) in combination with insulin degludec for basal insulin coverage
  - AID Control: CSII pump with an AID algorithm using an RAA for all bolus (mealtime and correction) and basal insulin coverage

#### 2.2 Secondary Objectives

The secondary objectives of this study are:

- To evaluate the safety of study treatment based on hypoglycemia event rate and severe hypoglycemia incidence rate in adults ≥18 years of age with T1DM for each of the three following groups:
  - o Afrezza + AID
  - Afrezza + Insulin Degludec
  - AID Control
- To evaluate the impact of study treatment on overall glycemic control when comparing baseline versus end of treatment period as measured by core CGM metrics:
  - Change in percent time in range (TIR), defined as time spent with glucose in the range of 70 to 180 mg/dL
  - Change in percent time below range (TBR), defined as time spent with glucose
     mg/dL
  - Change in percent time spent with glucose <54 mg/dL

  - Change in percent time above range (TAR), defined as time spent with glucose
     180 mg/dL
  - Change in percent time spent with glucose >250 mg/dL
  - o Change in glycemic variability as measured by coefficient of variation (CV)
- The above metrics to be evaluated on each of the three following groups in adults ≥18 years of age with T1DM for each of the three following groups:
  - o Afrezza + AID
  - o Afrezza + Insulin Degludec
  - AID Control

Confidential Page 21 of 70

#### 3 INVESTIGATIONAL PLAN

#### 3.1 Overall Study Design and Plan

[figure not shown]
MKC-TI-192 is a Phase 4, 90-day, randomized, three-arm, multicenter clinical trial evaluating the treatment paradigm and efficacy of Afrezza in controlling postprandial glucose in adult subjects (≥18 years of age) with T1DM. Subjects will be randomized to one of three treatment groups (two Afrezza groups and one control group):

- Afrezza + AID: Subjects in this group will use Afrezza for their bolus (mealtime) insulin and a CSII pump with an AID algorithm using RAA for their basal and correction insulin coverage.
- Afrezza + Insulin Degludec: Subjects in this group will use Afrezza for their bolus (mealtime and correction) insulin and insulin degludec for basal insulin coverage.
- AID Control: Subjects in this group will use a CSII pump with an AID algorithm using RAA for all bolus (mealtime and correction) and basal insulin coverage (control group).

See Figure 1 for a schematic of the study design.

Confidential Page 22 of 70

Figure 1: MKC-TI-192 Study Schematic

 $AID = automated insulin delivery, CGM = continuous glucose monitor, CSII = continuous subcutaneous insulin infusion, FEV_1 = forced expiratory volume in 1 second, HbA1c = glycated hemoglobin A1c, T1DM = type 1 diabetes mellitus$ 

- a. The Screening Visit should be scheduled 10 days (+ 4 days) before the subject's expected date of randomization. Subjects will be provided with a blinded Dexcom G6 Professional CGM device at the Screening Visit, which they will use in addition to their own CGM device during the Screening Period. At Visit 2, blinded CGM data will be downloaded and CGM sensor wear evaluated. If CGM sensor wear time is inadequate, per the discretion of the Investigator, the Screening Period can be extended and sensor wear can be repeated once. The subject will return to the clinic 10 days (+ 4 days) later and, if sensor wear is adequate and all eligibility criteria met, be randomized to study treatment and proceed with the meal challenge.
- b. Only applies to subjects in the Afrezza + Insulin Degludec group who use a Medtronic 670G/770G system.

Confidential Page 23 of 70

The study is composed of up to 5 clinic visits (screening, 3 treatment visits, and an end-of-treatment visit) and 9 telephone visits:

- **Visit 1 (Screening):** At the Screening Visit, informed consent will be obtained and screening procedures performed. Laboratory values will be collected for HbA1c, creatinine and thyroid-stimulating hormone (TSH); a documented normal TSH or creatinine level within 6 months of screening can be used in lieu of testing. A baseline forced expiratory volume in one second (FEV1) measurement will be obtained. A Dexcom G6 Pro blinded CGM device will be placed on each subject. Subjects will continue to use their own CGM device in addition to the blinded CGM.
- Visit 2 (Randomization & Meal Challenge): At least 10 days (+ 4 days) after Visit 1, subjects will return for Visit 2. At this visit, the Investigator will evaluate for appropriate use of the blinded sensor and will download the blinded CGM data (CSV file). If sensor wear time is inadequate, sensor wear can be repeated once and this becomes an unscheduled visit. The subject will return to the clinic 10 days (+ 4 days) later, and if the sensor wear is adequate and all eligibility criteria are met, be randomized to study treatment and proceed to the meal challenge and other Visit 2 assessments.

Subjects will be randomized in a 2:2:1 ratio to the following treatment groups, with the goal of 25 subjects enrolled:

- o Afrezza + AID (N=10)
- Afrezza + Insulin Degludec (N=10)
- o AID Control (N=5)

In order to achieve balanced representation of Medtronic 670G or 770G and Tandem Control IQ AID users for each group, the minimum subject numbers will be as follows:

- At least 5 subjects using Medtronic 670G or 770G
- o At least 5 subjects using Tandem Control IQ

Subjects will come to the clinic fasting with no manual insulin bolus administered within the prior 4 hours. CGM reports and pump reports will be downloaded from V1 to V2 using Carelink for Medtronic CGM and pumps, CGM reports/data and pump reports/data will be downloaded from V1 to V2 using Clarity for Dexcom CGM and t:connect for Tandem pumps (

Confidential Page 24 of 70

- ). The site will de-identify all reports and data. Subjects will undergo a 2-hour meal tolerance test in the clinic. The Afrezza + Insulin Degludec and the Afrezza + AID groups will be administered an Afrezza initial dose that is 2 times the calculated RAA dose (based on their insulin-to-carbohydrate ratio [I:CHO] calculated prandial dose) rounded down to the nearest 4-unit dose of Afrezza, but not exceeding 24 units of Afrezza. The Afrezza dose will be administered at the start of the meal challenge. The AID Control group will administer bolus insulin  $10 \pm 5$  minutes (per label) prior to the meal, per Investigator discretion. The start of the meal will define t=0. Subjects in the Afrezza + Insulin Degludec will continue on AID throughout the meal tolerance test and then transition to insulin degludec at the discretion of the Investigator. Basal insulin doses and time of administration in all study subjects will be documented. Subjects should have glucagon available for use in the event of hypoglycemia and should not be discharged until hypoglycemia is resolved.
- Visits T3, T4, T5, T6, T7, T8 (Telephone): Between Visits 2 and 9 in the clinic, several telephone visits will be conducted. During these visits, the Investigator will titrate insulin dosages, ask about changes to concomitant medications, record any AEs and hypoglycemic events, and answer any questions/concerns raised by the subject.
- Visit 9 (Clinic): This visit will be conducted at least 30 days (+7 days) after Visit 2. CGM reports and pump reports will be downloaded from V2 to V9 and from 10 days prior to V9 to V9 using Carelink for Medtronic CGM and pumps, CGM reports/data and pump reports/data will be downloaded from V2 to V9 and from 10 days prior to V9 to V9 using Clarity for Dexcom CGM and t:connect for Tandem pump). The site will de-identify all reports and data. The Investigator will titrate insulin dosages. Basal insulin dosages will be documented.
- Visits T10, T11, T12 (Telephone): Between Visits 9 and 13 in the clinic, three telephone visits will be conducted. During these visits, the Investigator will titrate dosages and answer any questions/concerns raised by subjects.

**Visit 13 (Clinic):** This visit will occur 8 to 10 days prior to Visit 14. CGM reports and pump reports will be downloaded from V9 to 30 days after V9 using Carelink for Medtronic CGM and pumps, CGM reports/data and pump reports/data will be downloaded from V9 to 30 days after V9 using Clarity for Dexcom CGM and t:connect for Tandem pumps (

Confidential Page 25 of 70

). The site will de-identify all reports/data. The Investigator will place a Dexcom G6 Pro blinded sensor on subjects in all groups. The Investigator will titrate insulin dosages. Additionally, Afrezza + AID and Afrezza + Degludec groups will be asked to log meal announcements and Afrezza doses in the final 10 days.

**Visit 14 (Clinic):** At least 90 days following Visit 2 (+ 7 days), subjects will return for HbA1c measurement and safety assessments, including a final FEV1 measurement. The Investigator will download the blinded CGM data (CSV file) from the prior sensor wear. Additionally, CGM reports and pump reports will be downloaded from 30 days before V14 to V14 and from V13 to V14 using Carelink for Medtronic CGM and pumps, CGM reports/data and pump reports/data will be downloaded from 30 days before V14 to V14 and from V13 to V14 using Clarity for Dexcom CGM and t:connect for Tandem pumps (

Confidential Page 26 of 70

). The site will de-identify all reports and data. Basal insulin dosages will be documented. See Section 3.7 for information on the assessments to be performed at these visits.

#### 3.2 Study Duration

The length of the entire study (from first subject enrolled to the last subject last visit) is expected to be 180 days. The end of the clinical study is defined as the day the last subject completes his/her last visit.

#### 3.3 Selection of Study Population

The population sought for this study is adult subjects ≥18 years of age with T1DM. Twenty-five subjects are planned to complete the study. Subjects who discontinue from the study within the first 4 weeks will be replaced. Subjects who discontinue from the study after 4 weeks will not be replaced. If possible, HbA1c measurements will be obtained for subjects who discontinue after 4 weeks of participation.

#### 3.3.1.1 Inclusion Criteria

Subjects must meet all of the following inclusion criteria to be eligible to participate in the study:

#### At screening:

- 1. Subjects ≥18 years of age at the time of signing the informed consent form
- 2. Clinical diagnosis of T1DM
- 3.  $\geq 7.0\%$  and  $\leq 11.0\%$  HbA1c
- 4. Treatment with a CSII pump with an AID algorithm (Medtronic 670G/770G or Tandem Control IQ) for at least 3 months, including use of the AID automated mode function
- 5. Ability to pay for their own RAA used in the insulin pump or injections, either through copay or self-pay, for the duration of the study (See acceptable insulin analogs in Section 3.4.2)
- 6. Willingness to follow study procedures including discontinuing their insulin pump and transitioning to insulin degludec injections plus Afrezza

#### 3.3.1.2 Exclusion Criteria

Subjects meeting any of the following exclusion criteria at screening will not be enrolled in the study.

#### At screening:

- 1. A recent history of asthma (defined as using any medications to treat within the last year), chronic obstructive pulmonary disease (COPD), or any other clinically important pulmonary disease (e.g., cystic fibrosis, bronchopulmonary dysplasia), or significant congenital or acquired cardiopulmonary disease
- 2. History of serious complications of diabetes (e.g., active proliferative retinopathy or symptomatic autonomic neuropathy)
- 3. History of hypersensitivity to insulin or any of the Afrezza excipients
- 4. On dialysis
- 5. Respiratory tract infection within 14 days before screening (subject may return 14 days after

Confidential Page 27 of 70

- resolution of symptoms for rescreening)
- 6. Exposure to any investigational drug in the past 30 days or an investigational device in the past 2 weeks
- 7. Adrenal insufficiency, active use of steroids or planned steroid use
- 8. Hypothyroidism not controlled, as defined by TSH outside the upper limit of the reference range by  $>1.5 \times$  in the last 6 months, according to the local laboratory reference range
- 9. Hyperthyroidism not controlled, as defined by TSH below the normal reference range, according to the local laboratory
- 10. Use of antiadrenergic drugs (e.g., beta blockers and clonidine)
- 11. Any concurrent illness (other than diabetes mellitus) not controlled by a stable therapeutic regimen
- 12. History of a significant eating disorder (e.g., anorexia or bulimia nervosa)
- 13. Current drug or alcohol abuse or a history of drug or alcohol abuse that, in the opinion of the Investigator or the Sponsor, would make the subject an unsuitable candidate for participation in the study
- 14. History of smoking (includes cigarettes, cigars, pipes, vaping devices, and marijuana) in the 6 months before screening
- 15. Female subject who is pregnant, breast-feeding, intends to become pregnant, or is of child-bearing potential and not using adequate contraceptive methods as required by local regulation or practice (may include sexual abstinence)
- 16. An event of severe hypoglycemia, as reported by the patient, within the last 180 days before screening
- 17. An episode of diabetic ketoacidosis (DKA), as determined by the Investigator, requiring hospitalization within the last 180 days before screening
- 18. Exposure to Afrezza in the 30 days before screening
- 19. Abnormal TSH or creatinine levels above 2.0 mg/dL

Subjects who are unable to comply with the requirements of the study or who, in the opinion of the Investigator, should not participate in the study are not eligible. In addition, any subjects for whom Afrezza is contraindicated, based on the Afrezza prescribing information (Afrezza 2020), should not be enrolled in the study.

#### 3.3.1.3 Removal of Subjects from Therapy or Assessment

A subject will be considered to have completed the study when the subject completes the treatment visits and the end-of-treatment visit assessments.

If a subject discontinues from the study before completing all protocol-specified visits, an early-termination visit should be conducted as soon as possible to have the assessments shown in the Schedule of Assessments (Table 3).

Participation in the study is strictly voluntary. A subject or legally authorized representative has the right to withdraw from the study at any time and for any reason. If he/she chooses to withdraw, the Investigator must be informed immediately. The Investigator has the right to

Confidential Page 28 of 70

terminate participation of any subject at any time if the Investigator deems it in the subject's best interest. The Investigator should discuss the subject's withdrawal with the medical monitor beforehand, if possible. If not possible, the Investigator should discuss the withdrawal with the medical monitor within 24 hours of being informed of the decision.

For any subject who fails to return to the site, the Investigator should make every effort to contact the subject (e.g., contact the subject's family or private physician, review available registries or health care database) and to determine their health status. Attempts to contact the subject must be documented in the subject's study records (e.g., times and dates of attempted telephone contact, receipt for sending a registered letter, and a copy of the letter).

Subjects withdrawn from the study must not be re-included in the study. Their inclusion numbers must not be reused. Subjects withdrawn within the first 4 weeks will be replaced. However, subjects withdrawn from the study after 4 weeks will not be replaced. If possible, HbA1c measurements will be obtained for subjects who are withdrawn after 4 weeks of participation.

#### 3.3.1.3.1 Reasons for Discontinuation

The reason and circumstances for early termination will be documented in the subject's case report form (CRF). The reason for any early discontinuation should be indicated on this form. The primary reason for a subject's early study termination should be selected from the following standard categories of early termination:

- Adverse Event (AE): Clinical or laboratory events occur that, in the medical judgment of the Investigator could affect the subject's safety or well-being if treatment is continued. This includes serious (Section 4.1.2) and nonserious AEs regardless of relation to the study drug.
- Withdrawal of Consent: The subject desires to withdraw from further participation in the study in the absence of an Investigator-determined medical need to withdraw. If the subject gives a reason for withdrawing, it should be recorded in the CRF.
- *Treatment Noncompliance:* The subject fails to comply with the prescribed dosing of the study treatment after multiple attempts have been made to obtain compliance.
- *Major Protocol Violation*: The subject's findings or conduct fails to meet the protocol entry criteria or fails to adhere to the protocol requirements that are deemed to affect subject safety or the integrity of the study data.
- *Pregnancy:* If a subject becomes pregnant, she will be discontinued from the study.
- Smoking: The subject begins smoking or vaping, including smoking marijuana.
- *DKA*: The subject has 2 events of DKA.
- Lost to Follow-up: The subject stops coming for visits and study personnel are unable to contact the subject.
- *Other*: The subject discontinues from the study for a reason other than those listed above, such as termination of study by Sponsor.

If a subject discontinues from the study due to the ongoing severe acute respiratory syndrome coronavirus 2 (SARS-CoV-2) global pandemic, information should be captured on the CRF so this information can be summarized in the clinical study report at the end of the study, in line with the FDA Guidance on Conduct of Clinical Trials of Medical Products during COVID-19

Confidential Page 29 of 70

Public Health Emergency (FDA 2021). The reason for discontinuation should be recorded on the CRF as SARS-CoV-2/COVID-19, if applicable, and include as many details as possible.

For example, specific reasons may include, but are not limited to:

- The subject exhibits symptoms consistent with COVID-19 within the last 10 days (yes/no).
- The subject has a positive test result for SARS-CoV-2 (yes/no).
- The subject has neither symptoms nor a positive test but has chosen to discontinue treatment due to COVID-19 concerns.

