**Table 3: Schedule of Assessments** 

| Study Period  | Screen                      | Treatment Period |    |    |    |    |    |    |    |      |                 |      |     |             |      |
|---|-----------------------------|------------------|----|----|----|----|----|----|----|------|-----------------|------|-----|-------------|------|
| In-clinic Visit (V) Telehealth Visit (T)                  | V1                          | V2               | Т3 | T4 | T5 | T6 | T7 | T8 | V9 | T10  | T11             | T12  | V13 | V14         | ET c |
| Day   | Up to
28 Days            | 0                | 1  | 2  | 4  | 7  | 14 | 21 | 30 | 37 b | 44 b | 51 b | 80  | 90
(EOT) |      |
| Visit Window (Days)                                       | Before Random. a |                  |    |    |    | ±2 | ±2 | ±2 | +7 | ±2   | ±2              | ±2   | +2  | +7          |      |
| Informed consent  | X                           |                  |    |    |    |    |    |    |    |      |                 |      |     |             |      |
| Eligibility criteria confirmed                            | X                           | X                |    |    |    |    |    |    |    |      |                 |      |     |             |      |
| Demographics and medical history                          | X                           |                  |    |    |    |    |    |    |    |      |                 |      |     |             |      |
| Randomization   |                             | X                |    |    |    |    |    |    |    |      |                 |      |     |             |      |
| Physical examination, including weight and height         | X                           |                  |    |    |    |    |    |    |    |      |                 |      |     | X           | X    |
| Prior/concomitant medications                             | X                           | X                | X  | X  | X  | X  | X  | X  | X  | X    | X               | X    | X   | X           | X    |
| Smoking status and evaluation of pulmonary toxin exposure | X                           |                  |    |    |    |    |    |    |    |      |                 |      |     | X           | X    |
| Adverse events d  | X                           | X                | X  | X  | X  | X  | X  | X  | X  | X    | X               | X    | X   | X           | X    |

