| Dispense insulin
degludec and injection
supplies, as necessary
(Afrezza + Insulin
Degludec group only) |                             | X  |                  |    |    |    |    |    | X  |      |                 |      |     |             |      |
| Record basal insulin
dosages (Afrezza +
Insulin Degludec
group only)                                      |                             | X  |                  |    |    |    |    |    | X  |      |                 |      | X   | X           |      |
| Collect Afrezza unused inhalers and cartridges as well as any unopened bottles of insulin degludec                 |                             |    |                  |    |    |    |    |    |    |      |                 |      |     | X           | X    |

Page 39 of 70

AID=automated insulin delivery, CGM=continuous glucose monitoring, COVID-19=coronavirus 2019, EOT=end of treatment, ET=early termination, FEV1=forced expiratory volume in 1 second, HbA1c=glycated hemoglobin A1c, RAA=rapid-acting insulin analog, Random=randomization, Screen=screening, SMBG=self-monitored blood glucose, TSH=thyroid-stimulating hormone.

- a. The Screening Visit should be scheduled 10 days (+ 4 days) before the subject's expected date of randomization. When subjects return for Visit 2, blinded CGM data will be downloaded and CGM sensor wear evaluated. If CGM sensor wear time is inadequate, per the discretion of the Investigator, the Screening Period can be extended (this becomes an unscheduled visit) and sensor wear can be repeated once. The subject will return to the clinic 10 days (+ 4 days) later and, if sensor wear is adequate and all eligibility criteria met, be randomized to study treatment and proceed with the meal challenge and Visit 2 assessments. Visit 2 should be within 4 days of the end of the final sensor wear data (i.e., the CGM sensor with adequate wear time).
- b. The timing of telephone visits T10, T11, and T12 is relative to Visit 9 (T10 should occur 7 days [±2 days] from Visit 9, T11 is 14 days [±2 days] from Visit 9, and T12 is 31 days [±2 days] from Visit 9).
- c. A sample should be collected for HbA1c at the ET visit if the subject discontinues the study after 4 weeks of participation.
- d. Any adverse event that occurs after the subject enrolls in the study (consent date) will be recorded.

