## 3.7.5 Telephone Visits (T10-T12)

The timing of telephone Visits T10, T11, and T12 is relative to Visit 9. Visit T10 should occur 7 days (±2 days) from Visit 9, T11 is 14 days (±2 days) from Visit 9, and T12 is 31 days (±2 days) from Visit 9.

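### Starting to smoke or vape is a listed reason for early termination, but no smoking question is scheduled between screening and the end of treatment.

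*Protocol*

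**What the plan says.** Section 3.3.1.3.1 says that the primary reason for stopping early "should be selected from the following standard categories of early termination". One of these categories is Smoking: "The subject begins smoking or vaping, including smoking marijuana".

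At entry, exclusion criterion 14 is "History of smoking (includes cigarettes, cigars, pipes, vaping devices, and marijuana) in the 6 months before screening".

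The Table 3 row "Smoking status and evaluation of pulmonary toxin exposure" is marked at V1, V14 and ET, and is blank in every other column. Section 3.7.1 repeats the item for V1. The procedure lists for V2, T3-T8, V9, T10-T12 and V13 (Sections 3.7.2 to 3.7.6) contain no smoking item. The other mentions of a smoking query, in Sections 3.4.9.1 and 3.9.2.1, belong to the medical history, which Table 3 places at V1.

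Under Section 3.3.1.3 the Investigator may "terminate participation of any subject at any time" when this is in the subject's best interest, and should discuss a withdrawal with the medical monitor.

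**The concern.** The sponsor treats smoking as relevant in three places: as an exclusion, as an early-termination category and as an end-of-study item. Between screening and the end of treatment, however, nothing scheduled would bring it to light. A subject who starts smoking, has no symptoms and does not mention it receives the first inhaled dose at V2 and is next asked when treatment is ending. By then the answer cannot shorten Afrezza exposure.

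What is at stake is safety monitoring in the two Afrezza groups. Change in FEV1 is a safety endpoint (Section 5.4.1), and a start date for smoking would help a reader interpret an individual change. The primary endpoint and the sample size are not affected.

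**Working it through.** **Scheduled items.** The Table 3 smoking row has 15 cells, with marks at V1, V14 and ET only. Contacts strictly between V2 and V14 are T3-T8 (6) + V9 (1) + T10-T12 (3) + V13 (1) = 11. Including V2, 12 consecutive scheduled contacts have no smoking item.

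**Subjects concerned.** Afrezza + AID 10 + Afrezza + Insulin Degludec 10 = 20 of 25. The 5 AID Control subjects do not receive Afrezza (Section 3.4.5).

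**Does the V2 eligibility check fill the gap?** Table 3 marks eligibility at V1 and V2, but exclusion 14 looks back from screening. By its terms it does not cover smoking that starts between V1 and V2, a period of up to 28 days. The closing paragraph of Section 3.3.1.2 does let the Investigator judge a subject unsuitable, with no such look-back, but it schedules no question.

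**Present interval.** V1 to V14 is at least 10 + 90 = 100 days and at most 28 + 97 = 125 days. The part on treatment is 90 days, or up to 97 with the V14 window.

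**Interval with three added questions.** The nominal days are V2 = 0, V9 = 30, V13 = 80 and V14 = 90. T12 has two timings. The Table 3 header gives Day 51, but note b says "T12 is 31 days [±2 days] from Visit 9" and Section 3.7.5 says "T12 is 31 days (±2 days) from Visit 9", which is Day 30 + 31 = 61. Both are shown.

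| Questions added | Gaps to V14 (days) | Sum | Longest |
|---|---|---|---|
| None | 90 | 90 | 90 |
| V2, V9, V13 | 30, 50, 10 | 90 | 50 |
| V2, V9, T12 on Day 51 | 30, 21, 39 | 90 | 39 |
| V2, V9, T12 on Day 61 | 30, 31, 29 | 90 | 31 |

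**Visit windows.** V9 falls on Day 30-37 and V14 on Day 90-97.
- T12 at V9 + 21 ± 2 days (the Day 51 reading): earliest Day 49, so the longest gap is 97 - 49 = 48 days.
- T12 at V9 + 31 ± 2 days: earliest Day 59, so the longest gap is 97 - 59 = 38 days.
- V13: Section 3.1 says "This visit will occur 8 to 10 days prior to Visit 14". With V14 on Day 97, V13 can be as late as Day 89, and the gap from V9 is then 89 - 30 = 59 days.

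Section 3.7.6 also places V13 30 (+7) days after V2. That repeats the V9 timing and is not used here.

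**Which late contact.** A positive answer at V13 leaves only 8 to 10 days of exposure to avoid. At T12 it leaves a nominal 90 - 51 = 39 or 90 - 61 = 29 days. T12 is therefore the more useful third contact.

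**The case against.** The strongest case against is that the schedule is internally consistent. Section 3.3.1.3.1 is a list of reasons to record on the CRF, and listing a reason does not oblige the protocol to screen for it. Pregnancy does require discontinuation, yet after V1 it too is tested only as needed (Table 3, note g). The risk sections (1.3.1) do not name smoking, so the harm to an Afrezza user is not set out. The consent form, CRF and site operations manual are not available here, and they may already tell subjects to report smoking.

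Much of this stands. It makes the point a design choice with a small gain. It also means that a question without a stated response would achieve little, that a V13 question adds little, and that the 5 control subjects need not be asked.

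What does not stand is that existing routes already ask. Investigator judgement depends on the Investigator learning of the smoking. Section 3.4.9.2 describes concomitant treatments as prescription drugs, herbal products and over-the-counter medicines, and names neither tobacco nor vaping. Extra lung function testing under Section 3.9.2.5 needs respiratory symptoms, and scheduled FEV1 is also confined to V1, V14 and ET.

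A reader might infer something stronger: that the protocol requires removal of anyone who starts smoking, and has no means of applying its own rule. The text does not support that. The smoking entry lacks the removal wording given to pregnancy in the same list and to two DKA events in Section 3.9.2.7.

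**Conclusion.** The point holds as a low-cost, optional improvement to safety monitoring for the 20 Afrezza subjects. As written, no smoking question is scheduled before the first dose or during a nominal 90 days of treatment. Three added questions reduce the longest nominal gap to 39 or 31 days, depending on which T12 timing applies. With visit windows the figures are 48 or 38 days, against up to 97 now.

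A reader might go on to infer that trial results are biased or that a given number of new smokers will be missed. The documents give no rate of starting smoking, so no number can be claimed. The analysis is descriptive, and the sample size was not derived statistically (Section 5.6).

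The blank cells and the intervals are certain. The practical gain is less so: it assumes that subjects are not already told to report smoking, that they answer truthfully, and that a positive answer is acted on.

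**What to change.** For the Afrezza groups only, add a self-reported question on smoking or vaping, with a start date if positive, at three existing contacts:

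- V2, before the first dose, covering any start since screening;
- V9;
- T12, after settling whether it falls on Day 51 or Day 61.

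Ask smoking status only; the pulmonary toxin part of the Table 3 row need not be repeated. State the response as well: a positive answer prompts review by the Investigator and medical monitor under Section 3.3.1.3, and the Smoking category is used if the subject is stopped. Whether to stop remains a clinical decision.

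The cost is one short question and two CRF fields (status and start date), or 20 × 3 = 60 answers if all 20 subjects attend all three contacts. It also needs a Table 3 amendment with IRB approval (Section 6.1.2). No new visit, test or analysis is required. Repeating a short check is feasible: Table 3, note j, already has sites check meal announcements in the Afrezza + AID group at every visit. Self-report will miss a subject who conceals smoking.
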